# Table 23Summary of blood sampling timepoints/immunological assays
(Amended 12 April 2005)

Blood sampling timepoint			Test	No. subjects	Laboratory	Priority
Timing	Timepoint	Clinic Visit No.			_	Rank
Des Dess 1	Screening	1	Anti-HBs antibodies	<del>200</del> 220	GSK Bio*	3 2
			Anti-CS antibodies	<del>200</del> 220	GSK Bio*	2 4
Pre Dose 1			Anti-Pertussis Antibodies	200	GSK Bio*	1
			СМІ	<del>200</del> 220	CISM	4 3
Post Dose 1	Month 0	4	<del>Determinants of Vaccine</del> <del>Response</del>	<del>200</del>	<del>CISM*</del>	4
	Month 3	9	Anti-PRP antibodies	<del>200</del> 220	GSK Bio*	1
Doot Doop 2			Anti-Pertussis antibodies	<del>200</del> 220	GSK Bio*	2
Post Dose 3			Anti-Diphtheria antibodies	<del>200</del> 220	GSK Bio*	3
			Anti-Tetanus antibodies	<del>200</del> 220	GSK Bio*	4
	Month 3½	Nonth 3½ 10	Anti-HBs antibodies	<del>200</del> 220	GSK Bio*	2
Post Dose 3			Anti-CS antibodies	<del>200</del> 220	GSK Bio*	1
			СМІ	<del>200</del> 220	<del>GSK Bio*</del> CISM	3
Post Dose 3	Month 6	11	Anti-CS antibodies	<del>200</del> 220	GSK Bio*	1
			СМІ	<del>200</del> 220	CISM	2
Post Dose 3	Month 14	Month 14 12	Anti-HBs antibodies	<del>200</del> 220	GSK Bio*	1
			12	Anti-CS antibodies	<del>200</del> 220	GSK Bio*

\*or designated laboratory

CMI: cell-mediated immunity (Amended 12 April 2005)

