## 2.2. Secondary: Immunogenicity

- To demonstrate the non-inferiority of antibody responses to Hepatitis B, when administered as 3 doses of RTS,S/AS02D at 10, 14 and 18 weeks of age compared to the regimen of 3 doses of Engerix-B at the same ages.
- To describe antibody responses to the circumsporozoite (CS) antigen of the RTS,S/AS02D malaria candidate vaccine administered as 3 doses intramuscularly in the left thigh to infants at 10, 14 and 18 weeks of age

[figure not shown]
Refer to Section 10.2 for definitions of secondary endpoints for immunogenicity.

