#### 5.1.8. Rescue plan for Hepatitis B response

Antibody response to HBsAg will be determined 30 days after Dose 3 of RTS,S/AS02D or Engerix-B in infants. Infants who have not attained seroprotective levels of anti-HBs antibodies will be investigated further and their HBsAg measured to determine whether or not they are chronic carriers of hepatitis B virus. Chronic carriers are known to respond poorly to licensed hepatitis B vaccines and therefore may not benefit from additional doses of hepatitis B vaccine. Children who are not chronic carriers will be offered additional doses of the licensed vaccine. Children who are withdrawn, or drop out prior to the Day 104 will be invited to the Day 104 clinic visit (Clinic Visit 10) for safety monitoring and to assess their hepatitis B seroprotection status.

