# 10.5.2. Sample size for secondary endpoint immunology of Hepatitis B response

This study will compare the immunogenicity of RTS,S/AS02D to Engerix-B. A noninferiority approach will be used to calculate the power of the study for the comparison of seroprotection rates and geometric mean titers of anti-HBs antibodies. The assessment of the anti-HBs antibody immune response will be based on approximately 200 evaluable subjects (100 subjects per group). This sample size will have 90% power at a 2.5% significance level using a one-sided equivalence test of proportions when the proportion that are seroprotected in the control group (subjects vaccinated with Engerix-B) is at least 0.97 and the proportion in the RTS,S/AS02D group is 0.97 and the maximum allowable difference between these proportions that still results in equivalence (the range of equivalence) is 0.10 (PASS 2000, one sided equivalence test of proportions, alpha = 2.5%).

Similarly this sample size will provide 98.5% power to demonstrate at a 5% significance level using an equivalence of means test, that the lower limit of a two sided 95% confidence interval on the GMT ratio of anti-HBs antibodies (RTS,S/AS02D vaccine

group over Engerix-B vaccine group ) is greater than 0.5 (2 fold decrease). (PASS 2000, equivalence of means, alpha = 5%). The standard deviation used for this calculation was 0.52 (computed on log base 10 transformed titers) and was derived from a GSK Biologicals study (Malaria-034) on 67 subjects which received three doses of RTS,S/AS02D administered at a 0, 1, 2 months schedule.

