# 10.8.3.1. Assessment of non-inferiority Clinic Visit 10 (one month post Dose 3 of RTS,S/AS02D or Engerix-B)

For seroprotection rates (anti-HBsAg), the difference between both groups (RTS,S/AS02D – Engerix-B) will be calculated as well as the 95% CI around this difference. If the lower limit of the two-sided 95% CI is greater than –0.10, non-inferiority of RTS,S/AS02D compared to Engerix-B will have been demonstrated in this study.

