## **Rationale/background for changes:**

The CISM, GSK Biologicals and MVI teams have decided to remove assessment of Determinants of Vaccine Response from this study. All references to the assessment have been removed throughout the protocol.

In order to ensure that there is sufficient blood available to carry out Cell-Mediated Immunity assessment at protocol-defined timepoints it is necessary to raise the amount of blood to be collected at these timepoints from 1 mL to 2 mL. The sampling methodology is not specified per-protocol but is clarified in the informed consent documents.

A further elimination criterion has been added in order to ensure that children who fail to thrive will not receive experimental vaccine.

In order to assess the pertussis response it is necessary to account for maternally acquired immunity. Assessment of antibodies to pertussis at screening was omitted in previous versions of the protocol. This has been corrected in this amendment.

Text and a table have been added to help clarify the time periods between which different classes of oncomitant medications/treatments must be recorded.

A number of typographical errors that have been noticed since the previous amendment was finalized have been corrected in this version

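### Table 23 ranks descriptive anti-CS ahead of anti-HBs at Visit 10, although anti-HBs at that visit is the only formally tested and powered immunogenicity endpoint

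*Protocol*

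**What the plan says.** Table 23 in section 5.5.3 lists the immunological assays by visit with a priority rank. At Month 3½ (Visit 10) the two serology rows are "Anti-CS antibodies <del>200</del> 220 GSK Bio* 1" and "Anti-HBs antibodies <del>200</del> 220 GSK Bio* 2", where the final figure is the rank; CMI is third. Appendix H repeats the table under Amendment 2. At Month 14 the order is reversed: anti-HBs is rank 1 and anti-CS rank 2.

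The two antigens have different roles in section 2.2. For hepatitis B the objective is "To demonstrate the non-inferiority of antibody responses to Hepatitis B". For CS it is "To describe antibody responses to the circumsporozoite (CS) antigen". Section 10.8.3.1 places the test at Visit 10 and requires the lower limit of the two-sided 95% CI for the seroprotection difference to exceed -0.10. Section 10.5.2 contains the only immunogenicity sample-size calculations, both for anti-HBs, and states: "The assessment of the anti-HBs antibody immune response will be based on approximately 200 evaluable subjects".

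Section 5.1.8 uses the anti-HBs result from 30 days after Dose 3: "Infants who have not attained seroprotective levels of anti-HBs antibodies will be investigated further and their HBsAg measured". Section 10.7 does not replace missing immunogenicity values; the subject is left out of that analysis.

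The Visit 10 draw is a minimum of 2 mL, shared by blood count, biochemistry, blood film, both serologies, parasite genotyping and CMI (section 5.4). The Amendment 2 rationale in Appendix H explains that, to have enough blood for CMI, "it is necessary to raise the amount of blood to be collected at these timepoints from 1 mL to 2 mL".

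**The concern.** A priority rank has an effect only when a sample cannot support every assay. At Visit 10 the ranking then gives the serum to the descriptive endpoint before the tested one. At Month 14, where anti-HBs is a tertiary summary (section 10.3.2), it comes first. Anti-HBs therefore has priority where it matters least to the trial's conclusions and loses it where the formal comparison is made.

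Two things are at stake for a child whose sample supports one serology only. The child drops out of the non-inferiority comparison. The child also has no scheduled anti-HBs value on which section 5.1.8 can act: anti-HBs is not scheduled at Visit 11, and the next planned measurement is Month 14.

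**Working it through.** **1. Roles at Visit 10**

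| | Anti-HBs | Anti-CS |
|---|---|---|
| Objective (2.2) | demonstrate non-inferiority | describe |
| Test (10.8.3) | CI limit against -0.10 | none; percentage, GMT, reverse cumulative curves |
| Sample size (10.5.2) | yes | none |
| Triggers follow-up (5.1.8) | yes | no |
| Rank at Visit 10 (Table 23) | 2 | 1 |
| Rank at Month 14 (Table 23) | 1 | 2 |

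**2. The plan's own power figure**

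Inputs from section 10.5.2: 0.97 in both groups, margin 0.10, one-sided alpha 2.5%, 100 per group, stated power 90%.

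Farrington-Manning score test, asymptotic: power = Φ((0.10 − 1.96·se0)/se1).

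- Restricted estimates under a difference of −0.10 are 0.8836 and 0.9836, so se0 = √((0.8836·0.1164 + 0.9836·0.0164)/100) = 0.0345.
- se1 = √(2·0.97·0.03/100) = 0.0241.
- Power = Φ((0.10 − 0.0676)/0.0241) = Φ(1.34) = 91.0%.

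The stated 90% is reproduced.

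**3. Results lost**

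The protocol gives no rate of insufficient serum and no serum volume per assay. I assume that 5-15% of Visit 10 samples support one serology only. The base is about 200 infants, because section 10.5 expects 10% of the 220 to be lost.

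- 200 × 5% = 10 anti-HBs results lost
- 200 × 15% = 30 anti-HBs results lost

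**4. Power after the loss**, at 0.97 versus 0.97

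| Per group | Loss | Exact, Newcombe CI | Farrington-Manning, asymptotic |
|---|---|---|---|
| 100 | 0% | 93.3% | 91.0% |
| 95 | 5% | 92.1% | 89.2% |
| 90 | 10% | 90.8% | 87.1% |
| 85 | 15% | 88.6% | 84.6% |

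**5. Non-seroprotected infants not identified at Visit 10**

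The failure rate is also an assumption: 3% (from the 0.97 in section 10.5.2) up to about 8% (Engerix-B seroprotection was 91.9% in Malaria-026, Table 10, in children of 24 months and over).

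- Low: 10 × 3% = 0.3
- High, with 8% in the control half only and none in the RTS,S half (100% seroprotected in the same table): 15 × 8% = 1.2
- Ceiling, only if 8% applied to both arms: 30 × 8% = 2.4

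**6. Cost of swapping the ranks**

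The same losses would fall on anti-CS. On the log scale its GMT confidence interval widens by 1/√0.95 = 1.03 to 1/√0.85 = 1.08, about 3-8%.

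**The case against.** The strongest reply is that no shortage is documented. The protocol does not define the priority rank, state the serum needed per assay or predict a shortfall. Visit 10 also looks no worse supplied than other visits: Visit 12 plans a 1 mL minimum for blood count, biochemistry and both serologies, and Visit 9 plans 1 mL for four serologies plus film and genotyping. Section 5.5.3 even provides for storing unused serum. This stands, and it is why the size can only be given under an assumption. It does not explain why, if the rank is ever used, the descriptive assay should come first.

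The order also has a textual basis: section 5.5.3 names CS as the main serological measure. Appendix F, however, names HBs and CSP together as the principal measures, and the 5.5.3 wording does not fit the objectives in 2.2 or the test in 10.8.3.1.

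Three stronger readings are tempting, and the documents do not support them.

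- A reader might infer that the hepatitis B follow-up cannot reach an infant with a short sample. Nothing in the protocol forbids a repeat draw, Visit 11 collects another 2 mL, and stored serum may be used to assess the immune response. What is missing is a scheduled result before Month 14.
- A reader might infer that anti-CS can be given up because it is all-or-none. Every child in Malaria-034 was seropositive for anti-CS, but every child there was also seroprotected for anti-HBs (Tables 15 and 17), and the anti-CS GMT is not all-or-none.
- A reader might infer that the comparison would be underpowered or biased. The fall in power is modest. If RTS,S seroprotection is 100%, as in Malaria-026, power stays at about 100% at all the sizes shown. Nothing suggests that shortage would differ between blinded arms.

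**Conclusion.** The point holds as a minor mismatch. The Visit 10 ranks run against the protocol's own hierarchy of objectives, sample-size planning and follow-up. The consequence depends on a shortage rate that the protocol does not give.

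Under the assumed 5-15%, the tested comparison loses 10-30 results and a few points of power. About one non-seroprotected infant at most would go unidentified at Visit 10, unless the Engerix-B failure rate seen in older children applied to both arms. With no shortage, nothing is lost either way. The case for the change rests on its near-zero cost, not on a demonstrated loss.

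**What to change.** In Table 23 at Month 3½ (Visit 10), give anti-HBs rank 1 and anti-CS rank 2, and leave CMI at rank 3. This matches the anti-HBs-first order at Month 14. Align the sentence in section 5.5.3 that names CS as the main serological measure with section 2.2 and Appendix F, and carry the new order into the laboratory instruction.

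The change is two figures, one sentence and one instruction. No sample size, analysis, visit or clinical rule changes. The price is that infants with short samples lose a descriptive one-month anti-CS titer instead of an anti-HBs result.

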#### 6. INVESTIGATIONAL PRODUCTS AND ADMINISTRATION

#### 6.1. Study vaccines

The candidate vaccine to be used has been developed and manufactured by GSK Biologicals.

The Quality Control Standards and Requirements for the candidate vaccine are described in separate release protocols and the required approvals have been obtained.

Commercial vaccines are assumed to comply with the specifications given in the manufacturer's Summary of Product Characteristics.

Refer to Appendix G for details of vaccine supplies.

#### 6.1.1. RTS,S/AS02D candidate malaria and hepatitis B vaccine

#### RTS,S antigen presentation:

• The lyophilized antigen pellet contains 31.25 µg of RTS,S with 12.6 mg of sucrose as cryoprotectant per 3 mL monodose vial. The pellet is reconstituted with adjuvant in liquid form and 0.5 mL of reconstituted vaccine contains 25µg RTS,S.

#### AS02D adjuvant:

• AS02D contains 25 µg of MPL®, 25 µg QS21 (QS21 is a triterpene glycoside purified from the bark of Quillaja saponaria) and 125 µL of a proprietary oil-in-water emulsion in phosphate buffered saline per 0.5 mL, presented in prefilled syringes.

A dose of 0.5 mL will be delivered. The presentation of the reconstituted RTS,S/AS02D candidate malaria and hepatitis B vaccine is an opaque milky liquid.

#### 6.1.2. TETRActHib

TETRActHibTM is licensed by Aventis Pasteur, Lyon. The vaccine is presented as one vial of Act-HIB *Hemophilus influenzae* type b polysaccharide conjugated to tetanus protein as a powder and one pre-filled syringe (PFS) of D.T.COQ/D.T.P. (adsorbed diphtheria, tetanus and pertussis vaccine, Aventis Pasteur, Lyon). Prior to vaccination the D.T.COQ/D.T.P. is mixed with the Act-HIB powder.

The vaccine composition is;

#### Act-HIB (Powder for one vaccinating dose)

- *Hemophilus influenzae* type b polysaccharide conjugated with tetanus protein 10 µg
- Sucrose and trometamol

#### D.T.COQ/D.T.P. (Suspension for injection for one vaccinating dose (0.5 mL)

•	Purified diphtheria toxoid	not less than 30 IU
•	Purified tetanus toxoid	not less than 60 IU
•	Bordetella pertussis	not less than 4 IU

• Aluminum hydroxide, thiomersal and buffer solution containing sodium chloride, dihydrate sodium hydrogen phosphate, potassium dihydrogen phosphate, acetic acid and/or sodium hydroxide and water for injections.

A dose of 0.5 mL will be delivered. The presentation of the reconstituted TETRActHib vaccine is a whitish cloudy liquid.

#### 6.1.3. Engerix-B

The pediatric dosage vial contains  $10 \ \mu g$  of purified major hepatitis B surface antigen. It is prepared as a suspension of 0.5 mL volume per vial. The content, upon storage may present a fine white deposit with a clear colorless supernatant. Once shaken, the vaccine is slightly opaque.

#### 6.2. Dosage and administration

#### 6.2.1. RTS,S/AS02D (0.5 mL dose)

RTS,S/AS02D will be supplied such that the reconstituted vaccine volume will provide a 0.5 mL pediatric dose. One 0.5 mL dose will be aspirated from each vial and used.

Disinfect top of vaccine vial (pellet) with alcohol swabs and let dry. Inject complete contents of one PFS of diluent into vial of lyophilized vaccine. Remove and discard the syringe and needle under appropriate safety precautions. The pellet is then dissolved by gently shaking the vial. Wait for 1 minute to ensure complete dissolution of vial contents before withdrawing a sufficient volume to provide a 0.5 mL dose (volume required for RTS,S/AS02D) of the reconstituted vaccine solution using a fresh needle and syringe for injection. The reconstituted vaccine should be administered by slow IM injection, using a 25G needle with length of 1 inch (25 mm), in the left antero-lateral thigh within 4 hours of reconstitution (storage at 2°C to 8°C).

#### 6.2.2. TETRActHib (0.5 mL dose)

Disinfect top of *Hemophilus* type b conjugate vaccine vial with alcohol swabs and let dry. Inject complete contents of one pre-filled syringe (PFS) of D.T.P. suspension (D.T.COQ/D.T.P.) into vial of *Hemophilus* type b conjugate vaccine. Remove and discard the syringe and needle with appropriate safety precautions. Shake before use to obtain a homogenous suspension. The vaccine should be withdrawn using a fresh needle for injection. The reconstituted vaccine should be administered by slow IM injection, using a 25G needle with length of 1 inch (25 mm), in the right antero-lateral thigh (storage at 2°C to 8°C).

#### 6.2.3. Engerix-B (0.5 mL dose)

Disinfect the top of the vaccine vial with alcohol swabs and shake gently while letting the alcohol dry. Then withdraw, using a fresh syringe and needle the contents of the vial into a syringe for injection. Remove and discard the needle with appropriate safety precautions. Use a fresh needle for injection. The vaccine should be administered soon afterwards intramuscularly in the deltoid region, using a 25G needle with length of 1 inch (25 mm) in the left antero-lateral thigh (storage at 2°C to 8°C) (*Amended 12 April 2005*).

#### 6.3. Storage

# ALL VACCINE VIALS/PRE-FILLED SYRINGES (RTS,S, Engerix-B, D.T.P. suspension [D.T.COQ/D.T.P.] and *Hemophilus influenzae* type B), AND ADJUVANTS (AS02D) MUST BE STORED IN THE REFRIGERATOR (+2°C to +8°C) AND MUST NOT BE FROZEN.

All vaccines will be stored in a safe and locked place with no access for unauthorized personnel. Storage temperature will be monitored daily, according to SOPs at the investigator's site. An alarm system and a back-up refrigerator will be available in case of power failure/breakdown.

The study monitor must be contacted if the cold chain is broken (e.g. vaccines become frozen or refrigeration fails).

Storage conditions for transport of vaccines from country medical department or dispatch center to study sites or between sites are described in Appendix D.

#### 6.4. Treatment allocation and randomization

#### 6.4.1. Randomization of supplies

A randomization list will be generated at GSK Biologicals, Rixensart, using a standard SAS® (Statistical Analysis System) program and will be used to assign the vaccines to treatment numbers. A 1:1 randomization of RTS,S/AS02D to Engerix-B will be used throughout the study.

#### 6.4.2. Randomization of subjects

Subjects will be allocated sequentially to treatment numbers in the order that they present for vaccination.

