### 1.3.3.3.1. Primary Efficacy Endpoint, Malaria-026

The Primary Efficacy Endpoint of the trial was the determination of the VE against clinical malaria disease and was evaluated in Cohort 1. The malaria Case Definition for the Primary Efficacy Endpoint was 'the presence of *P. falciparum* asexual parasitemia above 2500 per  $\mu$ L on Giemsa stained thick blood films and the presence of fever (axillary temperature  $\geq$  37.5°C) at the time of presentation and occurring in a child who is unwell and brought for treatment to a healthcare facility'.

In Cohort 1 and Cohort 2 the RTS,S/AS02A and control groups were well-balanced for age, gender, bednet usage, distance of residence from health facility and geographical area of residence. Malaria transmission intensity, as indicated by Hct, prevalence of splenomegaly and IFAT, was higher in Ilha Josina where Cohort 2 was evaluated than Manhiça where Cohort 1 was evaluated. Malaria transmission was not constant over the six-month period. Malaria disease rates in the control group were lower in the second half of the observation period.

VE was determined over a six-month surveillance period commencing from 14 days post Dose 3. As specified per RAP, the time at risk was adjusted for malaria drug usage, residence in the study, withdrawal and death and the estimate of effect was adjusted for the covariates of age of the subject, geographical area of the residence of the subject, bednet use, and distance of the subject's residence from the nearest health center. The estimate of VE determined as the time to the first clinical episode in the ATP Cohort for Efficacy (i.e. all children who received full vaccination courses and contributed to the time at risk) was 26.9% (95% CI 7.4% to42.2%; p=0.009) and after adjustment for covariates was 29.9% (95% CI 11.0% to 44.8%; p=0.004).

No waning of efficacy over the 6-month observation period was noted for the primary endpoint when analyzed by different methods (test for proportionality of hazards with Schoenfeld residuals, p=0.139).Consistent with these data, at the cross-sectional survey 6.5 months after Dose 3, prevalence of parasitemia in recipients of RTS,S/AS02A was 37% lower than in the recipients of control vaccines; 11.9% in RTS,S/AS02A vs 18.9% in controls, p=0.0003). Parasite densities in these children were similar between RTS,S/AS02A recipients and controls (geometric mean density 2271 vs 2513; p=0.699).

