# 3. STUDY DESIGN OVERVIEW

- Phase I/IIb, single-center, double blind (observer blind, participant blind), randomized controlled trial with two groups in one study site.
- Two hundred and twenty children will be enrolled.

Vaccine	Age (weeks)	Number of infants to be enrolled	Estimated number evaluable
TETRActHib	8, 12, 16	110	100
RTS,S/AS02D	10, 14, 18		
TETRActHib	8, 12, 16	110	100
Engerix-B	10, 14, 18		

- Prior to study start, a community information program will inform the local population of the study. Throughout the period of enrollment study information will be presented at antenatal clinics to expectant mothers.
- Infants at high risk of vertical transmission of hepatitis B infection will be excluded from this trial of an experimental hepatitis B vaccine. These infants will receive a licensed hepatitis B vaccine in a schedule beginning at birth. The woman's full signed informed consent will be required for antenatal HBsAg testing.
- The HIV infection rates of women presenting to antenatal clinics in the Manhiça area is currently approximately 20%. Infants of HIV positive women will be excluded to avoid obscuring the safety pattern associated with the investigational vaccine. The woman's full signed informed consent will be required for antenatal HIV testing.
- Healthy male and female infants aged 6 to 12 weeks will be screened. Those determined to be eligible, based on the inclusion and exclusion criteria, will be enrolled in the study.
- Infants enrolled for the study attending for the first injection of DTPw will be identified at EPI clinics and, if they meet the inclusion criteria, their parent(s)/guardian(s) asked for consent to the trial.

• Route of administration: all vaccines will be administered by the intramuscular route to the antero-lateral thigh.

Left thigh: RTS,S/AS02D or Engerix-B

Right thigh: TETRActHib

- Each infant will be observed for at least 60 minutes after vaccination with RTS,S/AS02D or Engerix-B to evaluate and treat any acute adverse events
- Oral Polio Vaccine will be provided and administered according to the recommended national guidelines (at birth, and coadministered with TETRActHib at 8, 12 and 16 weeks during the study).

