#### 4.1.5.2. Ilha Josina Health Center

Ilha Josina Health Center is the closest health center for <del>all</del> *most* study children. It does not have inpatient facilities. Currently (October 2004) in addition to the government staff of 1 nurse and 1 midwife it is strengthened by study personnel: 1 Medical Agent (Agente de medicina), 1 microscopist and 2 field workers. Children requiring inpatient management will be transferred to Manhiça District Hospital (*Amended 29 June 2005*).

The *Ilha Josina* Health Center operates during normal office hours, but 24 hour assistance is available at the Health Center. A nurse and midwife live beside Ilha Josina Health Center and are contactable 24 hours a day. If subjects present to the *Ilha Josina* Health Center 'out of hours' the nurse or midwife can contact Manhiça District Hospital by telephone or radio and request an ambulance to pick up the patient and transfer them to Manhiça District Hospital (*Amended 29 June 2005*).

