#### 5.1.11. Vaccination process

The vaccines RTS,S/AS02D and Engerix-B will be packaged in identical boxes and will be identified by a treatment number. The unique treatment number will identify all doses of these vaccines administered to each subject. After randomization the treatment number assigns the subject to one group or another in a blinded way. The administration of the vaccine TETRActHib is not blinded; however it will be identified by a treatment number.

The treatment number will be issued sequentially at Clinic Visit 2. Each subject will retain the same treatment number for their subsequent vaccine doses. The treatment number will be recorded on the subject's Clinic Form after the vaccine has been administered; information from the Clinic Form is subsequently transferred to the Case Report Form. The Clinic Form and Case Report Form link the subject number and the treatment number.

• All vaccines will be administered by the intramuscular route to the antero-lateral thigh: left thigh RTS,S/AS02D or Engerix-B and right thigh TETRActHib. Subjects who receive their vaccination with in the incorrect leg will continue to receive subsequent blinded vaccinations of RTS,S/AS02D or Engerix-B and unblinded vaccinations with TETRActHib as normal. The fact that the vaccine was administered in the wrong limb will be documented and they will be eliminated from the According to Protocol Cohort for Safety.

Vaccinations will take place at the EPI clinic of Ilha Josina Health Center *and Taninga Health Center (Amended 29 June 2005)*. All vaccinations will be given by a qualified person; a nurse or a doctor or a 'medical agent of preventative medicine'. A staff member experienced in the resuscitation of children will be available at all vaccination sessions. Facilities and equipment will be available to give emergency treatment in the case of an anaphylactic reaction following administration of vaccines. All children will be observed for an hour after the administration of vaccine to evaluate and treat any acute adverse events.

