# 10.5.3. Sample size for secondary endpoint proof of concept

Assuming an attack rate of 75% in the Control Group over the 3-month surveillance period (Personal Communication [name] September 2004: data from a study performed in Ilha Josina in 2001, July to September in children 7 to 18 months), 100 evaluable subjects per group are needed in order to have 90% power to show a Vaccine Efficacy (=1-hazard ratio) of 45% (Pass 2000, Log rank Survival, alpha=0.05, based on the assumption that the hazard rates are proportional). This is equivalent to an attack rate in the Vaccinated Group of 53.3%. Using proportion of subjects with malaria infection over the surveillance period, a Vaccine Efficacy (=1-risk ratio) of 29% can be detected with 90% power.

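### With Taninga added as a second vaccinating center, neither the allocation nor the unadjusted efficacy analysis is stratified by center; if transmission differs, the crude efficacy estimate is attenuated and the log-rank test loses some power

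*Protocol*

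**What the plan says.** **Allocation.** Protocol 6.4.1: "A 1:1 randomization of RTS,S/AS02D to Engerix-B will be used throughout the study". Section 6.4.2: "Subjects will be allocated sequentially to treatment numbers in the order that they present for vaccination". Section 5.1.11 adds: "The treatment number will be issued sequentially at Clinic Visit 2". None of these names a stratum, a block size or a division of numbers between clinics.

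**Centers.** Section 5.1.11 reads "Vaccinations will take place at the EPI clinic of Ilha Josina Health Center" and, since the June 2005 amendment, goes on to name Taninga Health Center. Section 4.1.5.5 has immunization clinics running every weekday at both. Section 6.4 was not revised with that amendment, and Section 3 keeps the label "Phase I/IIb, single-center, double blind (observer blind, participant blind), randomized controlled trial with two groups in one study site". Section 4.1.5.2 begins "Ilha Josina Health Center is the closest health center for" and, as amended, continues with most rather than all study children. It gives no proportion.

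**Analysis.** Section 10.9.3.2 compares the two groups by log-rank test, or by Wilcoxon if efficacy varies with time, and fits Cox models giving crude and adjusted estimates. Section 10.9.3.3 puts the estimate based on treatment group alone first. The second is adjusted for age, barrio (categorical) and distance from the health center. Center is not used in the test or in the first estimate.

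**Sample size.** Section 10.5.3: "Assuming an attack rate of 75% in the Control Group over the 3-month surveillance period". It cites a 2001 study in Ilha Josina as the source and derives 100 evaluable infants per group for 90% power at a vaccine efficacy (VE) of 45%.

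**The concern.** Section 6.4 describes allocation as for a single clinic, and a second clinic has since been added. Where infants live plausibly affects how soon they are infected. The introduction says of the sponsor's earlier trial (1.3.3.3.1): "Malaria transmission intensity, as indicated by Hct, prevalence of splenomegaly and IFAT, was higher in Ilha Josina where Cohort 2 was evaluated than Manhiça". So localities in this district can differ, although that comparison does not involve Taninga.

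Two consequences follow if Taninga and Ilha Josina differ. First, the arms may by chance hold different shares of Taninga infants. Second, and more important, pooling infants with different baseline hazards in an unstratified proportional-hazards analysis moves the hazard ratio toward 1. The crude VE is then smaller than the VE within each center, and the log-rank test is weaker than the calculation in 10.5.3 assumes. At stake is some of the 90% power for the proof-of-concept endpoint and the size of the efficacy figure reported first.

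**Working it through.** **1. The plan's own figure.** Inputs from 10.5.3: control attack rate 0.75, hazard ratio (HR) 0.55, alpha 0.05 (taken as two-sided), log-rank test.
- Vaccine-group attack rate: 1 − (1 − 0.75)^0.55 = 53.3%, as stated.
- Events (Freedman): (1.960 + 1.282)² × (1.55/0.45)² ≈ 125. Per arm: 125/(0.75 + 0.533) = 97.4.
- At 100 per arm, 128.3 events are expected: √128.3 × 0.45/1.55 − 1.960 = 1.33, so power is 90.8%.

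The 100 per group and 90% power reproduce.

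**2. Scenarios.** The protocol gives neither Taninga's share nor its transmission, so both are assumed: share *s* = 30%, 40% or 50%, and hazard at Taninga *r* = 1, 1/2, 1/3 or 1/4 of that at Ilha Josina. The Ilha Josina hazard λ over the surveillance period is set so that the overall control attack rate stays at 75%:

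(1 − s)(1 − e^−λ) + s(1 − e^−rλ) = 0.75

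Example, s = 0.3 and r = 0.5: λ = 1.732, giving control attack rates of 82.3% and 57.9%. Check: 0.7 × 82.3 + 0.3 × 57.9 = 75.0.

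**3. Simulation.** 200 infants, 1:1 allocation ignoring center, exponential times censored at the end of surveillance, true VE 45%. There were 6,000 trials per scenario (2,000 for the three-fold row, so Monte Carlo error is below 1 point of power).

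| Taninga hazard vs Ilha Josina | Taninga share | Crude VE | Crude power | VE stratified by center | Stratified power | Gain (points) |
|---|---|---|---|---|---|---|
| equal | 30% | 45.3% | 92.0% | 45.2% | 91.8% | −0.2 |
| equal | 50% | 45.4% | 92.4% | 45.4% | 92.2% | −0.2 |
| one half | 30% | 44.2% | 90.5% | 45.5% | 92.4% | 1.9 |
| one half | 50% | 43.8% | 90.3% | 45.7% | 93.0% | 2.7 |
| one third | 40% | 41.3% | 86.2% | 45.3% | 92.2% | 6.0 |
| one quarter | 30% | 40.7% | 84.4% | 45.7% | 93.0% | 8.6 |
| one quarter | 50% | 38.5% | 78.8% | 45.9% | 93.3% | 14.5 |

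The equal-rate differences are simulation noise. Repeating the three-fold case with Taninga at 30% and 50% gave gains of about 4.5 and 8 points. About 7–9 points is therefore a fair central figure for three- to four-fold, and it varies with the share.

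**4. Validity.** With no true effect, the crude log-rank test rejected in 4.6–5.3% of trials. The arms differed in Taninga share by 5–6 percentage points on average (95th percentile 12–14), in either direction at random.

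**5. Which change helps.** Stratifying the allocation by center (blocks of 4) while keeping the crude test changed power as follows:
- Equal rates: 92–93% against 92%.
- Two-fold: 91–92% against 90–91%.
- Four-fold: 83–87% against 79–84%.

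That is a gain of about 0–4 points. Stratifying the test gave 92–93% under either allocation. The loss therefore lies mainly in the analysis.

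**The case against.** **Locality is already in the plan.** The adjusted Cox model in 10.9.3.3 includes barrio and distance. If barrios lie largely within one center's catchment, it absorbs most of a center difference. A smaller simulation (600 trials per scenario, ten assumed barrios nested in the centers, two- and three-fold differences) gave adjusted VE of 46–47% and power of 91–94%, as good as stratifying by center. This stands, and it limits the point to the log-rank or Wilcoxon test and the estimate reported first. Further detail may sit in the reporting and analysis plan named in 6.5, but the protocol text as written is unstratified.

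**Transmission may not differ.** A reader might infer from 1.3.3.3.1 that center is a known, strong prognostic factor. That passage compares Ilha Josina with Manhiça, which is not a vaccinating center here, and 4.1.2 places both Ilha Josina and Taninga beside rivers. Center is a plausible prognostic factor and no more.

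**The larger scenarios are strained.** Holding the overall rate at 75% puts the Ilha Josina control rate at 82–96%, above the 75% observed there. Keeping Ilha Josina at 75% with Taninga at half the hazard gives 1 − 0.25^0.5 = 50% at Taninga and, at a 30% share, 0.7 × 75 + 0.3 × 50 = 67.5% overall. Having fewer events would itself lower power, and stratifying cannot restore that. That effect is not counted here.

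**Practicability.** A reader might infer that one number sequence cannot be run at two clinics. The text does not say that one run spans both. Boxes are labelled in advance, and each clinic could hold its own run and still allocate in order of presentation. The protocol is silent on this.

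**Stakes.** Unstratified 1:1 randomization is valid, and efficacy is a secondary, proof-of-concept objective. Both are true.

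**Conclusion.** The point holds as a low-cost improvement. The protocol now has two vaccinating centers, no center stratum in the allocation, and no use of center in the log-rank or Wilcoxon test or in the first Cox estimate. Balance within center is not guaranteed. A reader might infer that the arms will be unbalanced or the comparison biased. Neither follows: imbalance is random and usually small, and type I error is held.

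The size depends wholly on an assumed transmission difference: nothing at equal rates; about 2–3 points of power and 1–2 points of VE at two-fold, which still leaves about the stated 90%; about 7–9 points of power at three- to four-fold, reaching 14 in the most extreme scenario. It would be wrong to say that the stated power is missed, because no figure for Taninga exists in the protocol. The adjusted Cox estimate is largely protected already.

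**What to change.** **Main change, 10.9.3.2 (with 10.9.3.3):** stratify the log-rank or Wilcoxon test, and the Cox estimate reported first, by the health center where the infant was allocated a treatment number. Keep the estimate adjusted for age, barrio and distance as planned. This costs one sentence, uses a fact the site knows for every infant, and in simulation loses no material power if the centers turn out alike.

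**Secondary change, 6.4.2:** for infants not yet enrolled, give each health center its own consecutive run of treatment numbers made of whole 1:1 blocks, and say so. This balances only the remaining infants and adds little power, but it settles how numbers are divided between two clinics open on the same days. The small downside is holding spare numbers at two places.
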